During continuation cycles	In the presence of grade 4 neutropenia during continuation therapy, midostaurin/placebo must be held until ANC $\geq 1.0 \times 10^9/L$. Once ANC $\geq 1.0 \times 10^9/L$, then resume midostaurin/placebo at the previous dose. If neutropenia persists for more than two weeks, midostaurin/placebo study treatment must be discontinued.
Non-Hematologic toxicities:	
● Pulmonary toxicities	
During induction, consolidation and continuation cycles	For \geq grade 3 pneumonitis or interstitial lung disease without an infectious etiology, midostaurin/placebo must be interrupted for the remainder of the cycle. Resume midostaurin/placebo at the same dose when infiltrate resolves to \leq grade 1. Missed doses of midostaurin/placebo will not be made up. If the toxicity does not resolve to \leq grade 1 within 28 days after midostaurin/placebo interruption, the patient must be discontinued from the study treatment.
● Cardiac Toxicity	
During induction, consolidation and continuation cycles	
 ● For QTcF interval > 470 ms and ≤ 500 ms, check magnesium and potassium levels and correct any abnormalities. If possible, stop any medications that may prolong the QTcF interval. Midostaurin/placebo dose must be decreased to 50 mg once daily for the remainder of the cycle. Resume midostaurin/placebo at the initial dose in the next cycle provided that QTcF interval improves to ≤ 470 ms at the start of that cycle. Otherwise continue midostaurin/placebo 50 mg once daily. ● For QTcF interval > 500 ms and/or QTcF prolongation >60 ms from baseline, check magnesium and potassium levels and correct any abnormalities. Midostaurin/placebo must be held or interrupted for the remainder of the cycle, and, if possible, stop any medications that may prolong the QTcF interval. If QTcF improves to ≤ 470 ms just prior to the next cycle, resume midostaurin/placebo at the initial dose. If QTcF interval is not improved in time to start the next cycle, midostaurin/placebo may be held up to 28 days. If there is no improvement of QTcF to ≤ 470 ms within 28 days after midostaurin/placebo interruption, the patient must be discontinued from study treatment.
● Other Non-Hematologic toxicity	

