During consolidation cycles	
Contributions of concomitant medications to neurotoxicity should be assessed and other medications discontinued if possible.
 
For neurotoxicity \geq grade 2 due to high-dose cytarabine during consolidation therapy, discontinue high-dose cytarabine for the remainder of the cycle.
 
High-dose cytarabine may be considered at the next consolidation therapy cycle with a dose modification from 3000 mg/m² to 2000 mg/m² if the toxicity has resolved to \leq grade 1.
	
For any grade 2 or higher central nervous system AE (neurotoxicity) that is attributed by the investigator to HiDAC, this drug should not be used for further treatment.
 
If there are any following AEs in a given cycle that are attributed by the investigator to be related to HiDAC, the number of days of administration of HiDAC should be decreased as described below. Once the dose is reduced, the dose may not be re-escalated at any time even if there are no additional AEs occurring after the dose reduction.
 
Non-hematologic toxicity:
 
 Grade 3 (not including grade 3 anorexia, nausea, vomiting), decrease 1 day administration (4 days instead of 5 days) Grade 4, decrease 2 days administration (3 days instead of 5 days) 
Hematologic toxicity:
 
 Grade 4 febrile neutropenia with life threatening sepsis, decrease 1 day administration (4 days instead of 5 days) Delayed recovery of ANC and platelet (failure to reach ANC $\geq 1.0 \times 10^9/L$, platelet count $\geq 100 \times 10^9/L$ by Day 35 of treatment cycle), then decrease 1 day administration (4 days instead of 5 days)

			
• If ANC < $2.0 \times 10^9/L$ or platelet count < $150 \times 10^9/L$ just before administration, decrease cytarabine administration by 1 day (4 days instead of 5 days)
Dose modifications for daunorubicin due to hepatotoxicity (except in the setting of isolated Gilbert syndrome)			
		RATIFY regimen	JALSG regimen
During induction cycles	Total Bilirubin (mg/dL)	% daunorubicin dose to administer	% daunorubicin dose to administer
	≤ 2	100%	100%
	> 2 – ≤ 3.0	75% (25% dose reduction)	75% (25% dose reduction)
	> 3.0	50% (50% dose reduction)	50% (50% dose reduction)
All dose modifications should be based on the worst preceding toxicity. Common Toxicity Criteria for Adverse Events (CTCAE Version 5.0)			

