10.3 Treatments (study treatment, concomitant therapies, compliance)

The Safety set will be used for the analyses below. Categorical data will be summarized as frequencies and percentages. For continuous data, mean, standard deviation, median, minimum, and maximum will be presented.

The duration of exposure in day to study drug (midostaurin/placebo), daunorubicin and cytarabine as well as the dose intensity (computed as the ratio of actual cumulative dose received and actual duration of exposure) and the relative dose intensity (computed as the ratio of dose intensity and planned dose intensity) will be summarized by means of descriptive statistics using the safety set.

The duration of exposure for the study treatment will also be presented by chemotherapy regimen and treatment arm.

The number of patients with dose adjustments (reductions, interruption, or permanent discontinuation) and the reasons will be summarized by chemotherapy regimen and treatment arm and all dosing data will be listed.

Concomitant medications and significant non-drug therapies prior to and after the start of the study treatment will be listed and summarized according to the Anatomical Therapeutic Chemical (ATC) classification system, by treatment arm.

The number of regimens of the new anti-neoplastic therapy initiated after discontinuation of study treatment regardless of end of study treatment reason will be summarized for the FAS. In addition, the regimen of the next line of therapy, defined as the first new anti-neoplastic therapy initiated after discontinuation of study treatment regardless of end of study treatment reason, and its duration and best response will be summarized for the FAS.

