10.5.3.6 Tolerability

Tolerability of study drug will be assessed by summarizing the number of dose interruptions and dose reductions. Reasons for dose interruption and dose reductions will be listed by patient and summarized.

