### **Dose reductions, interruptions or permanent discontinuations**

The number of subjects who have dose reductions, permanent discontinuations or interruptions, and the reasons, will be summarized by cycle for induction and consolidation, treatment (induction, consolidation and continuation), and overall (only for the study drug), separately for each component of study treatment.

‘Dose change’, ‘Dose interrupted’, and ‘Dose permanently discontinued’ fields from the DAR eCRF will be used to determine the dose reductions, dose interruptions, and permanent discontinuations, respectively. The corresponding fields ‘Reason’ and ‘Reason for permanent discontinuation’ will be used to summarize the reasons.

A dose change is either ‘change in prescribed dose level’ or ‘dosing error’ where actual dose administered is different from the prescribed dose.

For the purpose of summarizing dose reduction, interruptions and their reasons, in case multiple entries for dose reduction/interruption that are entered on consecutive days with different reasons will be counted as separate reductions/interruptions. However, if the reason is the same in this mentioned multiple entries on consecutive days, then it will be counted as one reduction/interruption.

Dose reduction is defined as the dose change where the prescribed dose level is lower than the previous prescribed dose level or where the actual dose administered is lower than the calculated dose amount based on the prescribed dose. Therefore any dose change to correct a dosing error will not be considered a dose reduction. Because only dose change is collected in the CRF, dose reductions will be clarified programmatically using the definition above.

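### The SAP's dose-reduction rule does not cover fewer administration days, so JALSG high-dose cytarabine reductions are likely to be under-counted while RATIFY reductions are counted

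*SAP*

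**What the plan says.** **The rule.** SAP 2.4.2.1 (dose reductions, interruptions or permanent discontinuations) starts from the dose-change field of the dosing record: "A dose change is either ‘change in prescribed dose level’ or ‘dosing error’ where actual dose administered is different from the prescribed dose". Reductions are then picked out by program. The definition has two limbs. The first compares successive prescriptions: "Dose reduction is defined as the dose change where the prescribed dose level is lower than the previous prescribed dose level". The second compares what was given with what the prescription implies: "or where the actual dose administered is lower than the calculated dose amount based on the prescribed dose". A change that merely corrects a dosing error is not a reduction. The section gives no unit for dose level and does not mention number of days.

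**What is to be reduced.** Protocol Table 6-2 handles HiDAC differently in the two regimens.

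- JALSG: "the number of days of administration of HiDAC should be decreased as described below". Five triggers follow. Four lead to 4 days instead of 5, and one (grade 4 non-hematologic toxicity) leads to 3. The same cell calls the step a dose reduction and forbids later re-escalation.
- RATIFY: HiDAC "may be considered at the next consolidation therapy cycle with a dose modification" from 3000 to 2000 mg/m².

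For midostaurin/placebo, one QTcF step says that the "dose must be decreased to 50 mg once daily for the remainder of the cycle".

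**What is to be reported.** Protocol 10.3: "The number of patients with dose adjustments (reductions, interruption, or permanent discontinuation) and the reasons will be summarized by chemotherapy regimen and treatment arm". Protocol 10.5.3.6: "Tolerability of study drug will be assessed by summarizing the number of dose interruptions and dose reductions".

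**The concern.** The protocol reduces HiDAC in two ways, by mg/m² in RATIFY and by days in JALSG. The SAP definition is written for the first. If dose level means the dose per administration, a JALSG patient moved from 5 days to 4 has the same prescribed level as before and receives exactly the calculated amount at each infusion. Neither limb applies.

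Protocol 10.3 asks for a comparison across regimens, and the count would then use different effective definitions on its two sides. JALSG is also where the information is most wanted: Protocol 2.1 says there is no large experience of midostaurin with this regimen and that this study is to supply it. A reader of the table could conclude that JALSG consolidation was better tolerated than it was, and the reasons for the cuts would be missing from the summary meant to show them.

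Day cuts need not be rare. One trigger is ANC below 2.0 or platelets below 150 (×10⁹/L) just before administration, whereas a consolidation cycle may begin from ANC 1.0 and platelets 100 (Protocol 6.1.1.1). Counts between those values satisfy both statements. The documents give no expected frequency.

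**Working it through.** **Inputs.** HiDAC dose and schedule: Protocol 6.1.1.1, 6.1.1.2 and Table 6-1. Modifications: Table 6-2. Planned dose intensity (PDI), actual dose intensity (ADI) and relative dose intensity (RDI = ADI / PDI × 100): SAP 2.4.2.1.

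**Step 1. Reproduce the SAP's planned figures** (dose × infusions per day × days).

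- JALSG: 2000 × 2 × 5 = 20000 mg/m²/cycle, as stated.
- RATIFY: 3000 × 2 × 3 = 18000 mg/m²/cycle, as stated.

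**Step 2. Size of each modification.**

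- JALSG, 4 days: 2000 × 2 × 4 = 16000. RDI = 16000/20000 = 80%, a 20% loss.
- JALSG, 3 days: 2000 × 2 × 3 = 12000. RDI = 12000/20000 = 60%, a 40% loss.
- RATIFY, 2000 mg/m²: 2000 × 2 × 3 = 12000. RDI = 12000/18000 = 66.7%, a 33.3% loss.

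**Step 3. Apply the first limb (lower prescribed level) under each possible unit.**

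| Unit of dose level | JALSG 5 to 4 days | Counted? | RATIFY 3000 to 2000 | Counted? |
|---|---|---|---|---|
| per infusion (mg/m²) | 2000 vs 2000 | no | 2000 vs 3000 | yes |
| per day (mg/m²) | 4000 vs 4000 | no | 4000 vs 6000 | yes |
| per cycle (mg/m²) | 16000 vs 20000 | yes | 12000 vs 18000 | yes |

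The 3-day cut behaves as the 4-day cut does. The RATIFY step is counted under every unit; the JALSG step only under the per-cycle unit.

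**Step 4. Apply the second limb (actual below calculated).** Per infusion, actual equals calculated at 2000 mg/m², so it does not apply. Per cycle, if the prescription is written for 4 days, actual 16000 equals calculated 16000, so again it does not apply. It would apply per cycle only if the prescription still read 5 days.

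**Step 5. Which unit is natural?** Table 6-1 puts 2000 mg/m² per dose in the dose column and Days 1-5 in the frequency column. The SAP also gives a rule for merging reduction or interruption entries made on consecutive days, which implies records shorter than a cycle. Both point to a per-administration reading. In the other direction, the SAP expresses HiDAC intensity in mg/m²/cycle.

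**Step 6. Midostaurin/placebo.** Going from 50 mg twice daily to 50 mg once daily leaves mg per dose at 50 but moves the daily total from 100 to 50 mg. The SAP's PDI for study drug is 100 mg/day, so the daily reading is the likelier one and the step would count.

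**The case against.** The strongest reply has three parts.

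**The definition is wider than its first limb, and the form is unseen.** A reader might infer that the SAP counts a reduction only when the prescribed level falls, and that the table must show no JALSG HiDAC reductions whatever happened. The documents do not support that. The second limb exists. A JALSG patient aged 60 or older moved between cycles from 2000 to the optional 1500 mg/m² meets the first limb. On a per-cycle unit the day cuts count too. The dosing-record form is not in the documents, so a site might enter a dropped day as a dose change, an interruption or a discontinuation. This stands, and it limits the finding to a likely under-count.

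**The lost dose appears elsewhere.** RDI by cycle would read 80% or 60%. Exposure days by cycle are summarized by regimen. Every dose is listed with its change reason, and SAP 2.8.1 tabulates adverse events leading to dose reduction or interruption. This also stands, so the shortfall would not be hidden. But RDI is not a count of patients, carries no reasons and is not stated to be split by regimen. Exposure days include temporarily interrupted days, so a cut recorded as an interruption would still read 5. None of these replaces the table that Protocol 10.3 asks for.

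**It is one descriptive count.** This is correct. EFS, the success criterion, OS and the analysis sets are untouched.

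**Conclusion.** The point holds in a limited form. The SAP states a rule for identifying reductions that, on its natural per-administration reading, misses all five JALSG HiDAC day cuts, which the protocol itself calls dose reductions, while counting the RATIFY change. Cuts of 20% and 40% of the cycle dose would go uncounted beside a counted cut of 33%. The by-regimen comparison in Protocol 10.3 would be uneven, with JALSG reductions and their reasons understated.

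This rests on two assumptions: that dose level is per administration (or per day), and that sites do not code a shortened course in some other way that meets the definition. The number of patients affected cannot be derived from the documents.

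A reader might extend the criticism to the once-daily midostaurin step and its role in the tolerability summary. That is weak, because the SAP's mg/day unit already favors counting it. It merits a clarifying sentence only.

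**What to change.** In SAP 2.4.2.1, add:

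- For JALSG high-dose cytarabine, a consolidation cycle with fewer administration days than planned (5), or than the previous cycle, because of a Table 6-2 criterion is a dose reduction. It is reported with its recorded reason and is not also counted as an interruption.
- For midostaurin/placebo, dose level means total daily dose in mg/day, consistent with the PDI of 100 mg/day.

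The same mechanical rule should apply in both arms. The change affects reporting only and leaves dosing as it is. The cost is a few lines of SAP text and a small derivation from dosing records, provided that the reason for a shortened cycle was captured; that should be checked against the form.

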#### **2.4.2.2 Prior, concomitant and post therapies**

##### **Prior anti-cancer therapy**

The number and percentage of patients who received any prior anti-neoplastic medications, will be summarized by ATC class, preferred term and treatment. Summaries will include total number of regimens, setting, and reason for discontinuation of therapy. Prior anti-neoplastic medications will be listed.

Anti-neoplastic medications will be coded using the WHO Drug Dictionary (WHO-DD). Details regarding WHO-DD version will be included in the footnote in the tables/listings.

The above analyses will be performed using the FAS.

##### **Post treatment anti-cancer therapy**

Anti-neoplastic therapies since discontinuation of study treatment will be listed and summarized by ATC class, preferred term, and treatment group by means of frequency counts and percentages. The number of regimens of the new anti-neoplastic therapy initiated after discontinuation of study treatment regardless of end of study treatment reason will be summarized. In addition, the regimen of the next line of therapy, defined as the first new anti-neoplastic therapy initiated after discontinuation of study treatment regardless of end of study treatment reason, and its setting, duration and best response will be summarized.

The above analyses will be performed using the FAS.

##### **Concomitant medications**

Concomitant therapy is defined as all interventions (therapeutic treatments and procedures) other than the study treatment administered to a patient coinciding with the study treatment period. Concomitant therapy include medications (other than study drugs) starting on or after the start date of study treatment or medications starting prior to the start date of study treatment and continuing after the start date of study treatment.

Concomitant medications will be coded using the WHO-DD and summarized by ATC class and preferred term using frequency counts and percentages. The same analyses will be performed for strong CYP3A4 inhibitors. Surgical and medical procedures will be coded using MedDRA and summarized by SOC and preferred term. These summaries will include:

1. Medications starting on or after the start of study treatment but no later than 30 days after start of last dose of study treatment, and
2. Medications starting prior to start of study treatment and continuing after the start of study treatment.

All prior and concomitant therapies will be listed. Any concomitant therapies starting and ending prior to the start of study treatment or starting more than 30 days after the last date of study treatment will be flagged in the listing. The safety set will be used for all concomitant medication tables and listings.

### Hematopoietic Stem Cell Transplant (HSCT)

The number and percentage of patients who received SCT will be summarized by type of SCT (allogeneic related SCT, allogeneic unrelated SCT, autologous SCT, cord blood, and other) and treatment arm. According to [Table 2-3](#), type of SCT will be categorized based on source, transplanted type, and allogeneic donor type collected in eCRF page. A summary table will be produced by:

- Overall
- Occurred in patients without Complete Remission
- Occurred during first CR
- Occurred after relapse

The difference in SCT rates with its 95% confidence interval will also be provided.

The time to SCT (defined as the time from randomization to the date of SCT) overall and that occurred during first CR will be summarized by treatment arm.

The above analyses will be performed using the FAS.

**Table 2-3 Type of SCT**

Type	Source	Transplant type	Allogeneic donor type
Allogeneic related SCT	1) Other than cord blood	Allogeneic-full conditioning Allogeneic reduced conditioning	Sibling fully matched Sibling any mismatch
	2) Other than cord blood	Other than Autologous	Haploidentical
Allogeneic unrelated SCT	Other than cord blood	Allogeneic-full conditioning Allogeneic reduced conditioning	Unrelated fully matched Unrelated any mismatch
Autologous SCT	Other than cord blood	Autologous	Other than Haploidentical
Cord blood	Cord blood	Other than Autologous	Other than Haploidentical
Others	None of the above		

## 2.5 Analysis of the primary objective

### Safety evaluation part (Part 1, Japan only)

The primary objective for the part 1 is to evaluate the safety and tolerability of midostaurin in combination with chemotherapy in Japanese patients with newly diagnosed AML.

### Randomized part (Part 2)

The primary objective for the part 2 is to evaluate the efficacy based on event-free survival (EFS) of midostaurin versus placebo in combination with daunorubicin/cytarabine induction, with high-dose cytarabine consolidation, and with midostaurin single agent continuation therapy in newly diagnosed patients with FLT3-mutated AML.

## 2.5.1 Primary endpoint

### Safety evaluation part (Part 1, Japan only)

The primary variable for the part 1 in Japan is the incidence of Safety Events, defined as death or serious adverse event leading to treatment discontinuation that occurs on or before Day 21 of the first consolidation cycle and that is determined by the Independent Safety Committee to be definitely or probably related to midostaurin, among evaluable patients.

### Randomized part (Part 2)

The primary efficacy variable for the part 2 is event-free survival (EFS), defined as the time from the date of randomization until an EFS event is observed. An EFS event is defined as a failure to obtain a CR within induction 2, relapse after CR, or death due to any cause, whichever occurs first. Patients who do not complete first course of therapy without documented post-baseline CR should be considered a treatment failure. Clinical response (CR, CRp, PR and treatment failure, and relapse after CR) will be assessed via local review according to criteria defined in [Section 2.7.1](#). Relevant assessment date collected in the eCRF International Working Group (IWG) Response page will be used for the date of clinical response. For patients with treatment failure, the EFS will be documented as event at day 1 (refer to [Table 2-4](#)).

The final analysis for the part 2 will be based on FAS and will include all data observed up to the LPLV. If a patient has not observed EFS event at the LPLV, EFS will be censored at the date of the last adequate clinical assessment before the LPLV.

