7.2 Assessment types

7.2.1 Efficacy assessments

Disease assessments will be performed locally through evaluation of bone marrow specimens, peripheral blood samples, and other relevant data that will be collected as described in [Table 7-1](#). The response assessment will be according to Cheson criteria ([Cheson 2003](#)). Response assessments will require a bone marrow aspirate to be performed. In the event of a dry tap or an aspiration that is inadequate for interpretation, a bone marrow biopsy is required for response assessment.

Complete remission (CR): Complete remission is defined as all of the following:

- Peripheral Blood Counts
 - Absolute neutrophil count $\geq 1.0 \times 10^9/L$.
 - Platelet count $\geq 100 \times 10^9/L$.
 - No leukemic blasts in the peripheral blood.

- Adequate erythroid recovery so that RBC transfusions are not necessary.
- No Auer rods.
- Bone Marrow
 - Adequate cellularity.
 - No Auer rods.
 - < 5% blast cells.
 - No extramedullary leukemia (such as CNS or soft tissue involvement).

Morphologic complete remission with incomplete platelet count recovery (CRp)

- CRp satisfies all CR criteria except platelets < $100 \times 10^9/L$, but platelet transfusions are not necessary.

Partial Remission (PR)

- Must meet all criteria of a CR except that the bone marrow may contain 5%-24% blasts.

Treatment Failure

- Resistance disease:
 - Patient survives ≥ 7 days post chemotherapy; persistent AML in blood and bone marrow.
- Aplasia:
 - Patient survives ≥ 7 days post chemotherapy; death while cytopenic, with aplastic bone marrow
- Indeterminate cause:
 - Patient who die < 7 days post therapy
 - Patient who die > 7 days post therapy with no peripheral blood blasts, but no bone marrow examination
 - Patient who do not complete the first course of therapy

Relapse

Any of the following, occurring after CR:

- The reappearance of circulating blast cells not attributable to “overshoot” following recovery from myelosuppressive therapy.
- $>5\%$ blasts in the marrow, not attributable to another cause (e.g., CSF, bone marrow regeneration).
- Development of extramedullary leukemia.

Remission Induction cycle 1

For the first induction cycle, a bone marrow aspirate will be obtained from Day 21 to Day 28 to determine the presence of residual leukemia ($\geq 5\%$ blasts) according to Cheson criteria ([Cheson 2003](#)) and the need for a second induction cycle or CR.

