If the bone marrow aspirate is insufficient to make a determination of remission, then the bone marrow assessment should be repeated after about one week.

- If the Day 21 or subsequent bone marrow aspirations show $\geq 5\%$ leukemic blasts in a cellular marrow ($>20\%$) or otherwise meet criteria for persistent leukemia, then the patient will receive a second cycle of induction therapy.
- Patients for whom a CR is documented on Day 21-Day 28 BMA, will advance to consolidation therapy.
- In absence of “hematology recovery” (defined as ANC $\geq 1.0 \times 10^9/L$ and platelets $\geq 100 \times 10^9/L$) at the time of the Day 21-Day 28 bone marrow aspiration showing $<5\%$ leukemic blasts in a cellular marrow ($>20\%$), the patient will be observed until hematologic recovery and another bone marrow aspiration will be performed within about one week after recovery of ANC and platelets to document continued presence of CR. Physicians should consider earlier bone marrow exams in patients, as clinically indicated.

If a CR (as described in [Section 10.5.2.2](#)) is documented, then the relevant slides must be kept at the site.

Remission Induction cycle 2

For the second induction cycle, a bone marrow aspirate will be obtained from Day 21 to Day 28 to determine the presence of residual leukemia ($\geq 5\%$ blasts) or CR according to Cheson criteria ([Cheson 2003](#)).

If the bone marrow aspirate is insufficient to make a determination of remission, then the bone marrow assessment should be repeated after about one week.

- Patients for whom a CR is documented, will advance to consolidation therapy.
- In absence of “hematology recovery” (defined as ANC $\geq 1.0 \times 10^9/L$ and platelets $\geq 100 \times 10^9/L$) at the time of the Day 21-Day 28 bone marrow aspiration showing $<5\%$ leukemic blasts, the patient will be observed until hematologic recovery and another bone marrow aspiration will be performed within about one week after recovery of ANC and platelets to document continued presence of CR. Physicians should consider earlier bone marrow exams in patients, as clinically indicated.
- Patients failing to achieve CR will be discontinued from study treatment but will continue to be followed for survival.

If a CR (as described in [Section 10.5.2.2](#)) is documented, then the relevant slides must be kept at the site.

Consolidation therapy:

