10.4.1 Variable

The primary variable for the part 1 in Japan is the incidence of Safety Events, defined as death or serious adverse event leading to treatment discontinuation that occurs on or before Day 21 of the first consolidation cycle and that is determined by the Independent Safety Committee to be definitely or probably related to midostaurin, among evaluable patients.

The primary efficacy variable for the part 2 is event-free survival (EFS), defined as the time from the date of randomization until an EFS event is observed. An EFS event is defined as a failure to obtain a CR within induction 2, relapse after CR, or death due to any cause, whichever occurs first. Clinical response (CR, CRp, PR and treatment failure after CR) will be assessed via local review according to criteria defined in [Section 10.5.2.2](#). For patients with treatment failure, the EFS will be replaced to 1.

All efficacy analyses for the part 2 will be based on FAS and will include all data observed up-to the cut-off date. If a patient has not observed EFS event at the analysis cut-off date, EFS will be censored at the date of the last adequate clinical assessment before the cut-off date.

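### EFS counts any failure to reach CR by induction 2 as an event, but the coding tables give an event date only to 'Treatment failure', leaving CRp and PR without a row

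*SAP*

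**What the plan says.** **Definition.** SAP 2.5.1: "An EFS event is defined as a failure to obtain a CR within induction 2, relapse after CR, or death due to any cause". Protocol 10.4.1 defines the event in the same way.

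**Coding and dating.** Protocol 10.4.1: "For patients with treatment failure, the EFS will be replaced to 1". SAP 2.5.1: "For patients with treatment failure, the EFS will be documented as event at day 1". Protocol Table 10-1 and SAP Table 2-4 each have one row for this component, labelled *Treatment failure*, dated randomization + 1 and counted as an event. Neither table has a row for no CR, CRp or PR. SAP 2.5.1 adds one group: "Patients who do not complete first course of therapy without documented post-baseline CR should be considered a treatment failure".

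**Response categories.** SAP 2.5.1 lists them separately: "Clinical response (CR, CRp, PR and treatment failure, and relapse after CR) will be assessed via local review". In protocol 7.2.1:
- CRp meets every CR criterion except the platelet count.
- PR is a separate category: "Must meet all criteria of a CR except that the bone marrow may contain 5%-24% blasts".
- Treatment failure covers resistant disease ("persistent AML in blood and bone marrow"), death in aplasia, and indeterminate cause.
- Relapse is defined only after CR.

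**After induction 2.** Protocol 7.2.1: "Patients failing to achieve CR will be discontinued from study treatment but will continue to be followed for survival".

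**The concern.** The definition speaks of no CR; the derivation speaks of treatment failure. In protocol 7.2.1 the second is narrower than the first. A programmer who works from Table 2-4 and the recorded response category would give a patient ending induction 2 in CRp or PR a different outcome from the one the definition requires. A programmer who works from the definition would count an event, but would have to choose its date.

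This matters because the no-CR component is the largest part of EFS in A2301, and because the estimated HR is read against 1 with no alpha. A few patients coded differently in one arm can move the estimate noticeably in a trial of 62.

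**Working it through.** **1. Trace a patient who completes induction 2 in CRp or PR through Table 2-4.**
- *Treatment failure* row: does not apply, since 7.2.1 puts CRp and PR in their own categories. SAP 5.1.1.1 (incomplete efficacy dates) also groups CRp and PR with CR, apart from treatment failure and relapse.
- SAP 2.5.1 extension: does not apply, since the first course was completed.
- Relapse: cannot occur without a prior CR.
- Death at or before the next scheduled assessment, or after exactly one missing assessment: an event, but at the death date.
- Death after two or more missing assessments: censored. This is plausible in survival follow-up.
- Otherwise: *No relapse or death*, censored at the last adequate assessment.

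The definition makes the same patient an event. The pointers to the response criteria do not settle it: SAP 2.7.1 defines only OS, CR rate and CIR, and protocol 10.5.2.2 only the CR rate.

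**2. Size of the component (protocol Table 14-1).**
- Share of A2301 EFS events: (125 + 150)/521 = 275/521 = 52.8%.
- Expected non-CR patients among 62, at 31 per arm: 31 × 125/360 + 31 × 150/357 = 10.8 + 13.0 = 23.8.
- The documents do not give the share that is CRp, PR or marrow-only. Assuming 10-30%: 0.10 × 23.8 = 2.4 and 0.30 × 23.8 = 7.1, so about 2-7 patients.

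**3. The plan's own figure, then the effect of lost events.** The probability that the estimated HR is below 1 is approximately Φ(√(events/4) × |ln HR|). With HR 0.728 this gives 83.0% at 36 events (plan: 84.1%) and 81.9% at 33 events (plan: 82.7%). The plan resampled A2301 data, so small differences are expected. Holding the HR at 0.728 and removing the same share of no-CR events in both arms:

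| Assumed share | Events lost of 33 | Probability of HR < 1 |
|---|---|---|
| 0% | 0 | 81.9% |
| 10% | 1.7-2.4 | 81.3%-81.0% |
| 25% | 4.4-5.9 | 80.2%-79.5% |
| 50% | 8.7-11.9 | 78.3%-76.7% |

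The lower loss applies the 52.8% share to 33 events; the higher applies it to the 23.8 patients.

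**4. Effect on the HR estimate.** Simulation with 31 per arm and day-1 failures in 42% (placebo) and 34.7% (midostaurin). Later events are exponential with assumed medians of 16 and 19 months, and censoring is at 12-24 months. The Cox model is unstratified with Efron ties; 600 replicates. The affected patients are changed from a day-1 event to censored at 2 months.

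| Patients changed | All placebo | All midostaurin | Same number in each arm |
|---|---|---|---|
| 1 | × 1.06 | × 0.94 | × 0.99 |
| 2 | × 1.13 | × 0.88 | × 0.99 |
| 3 | × 1.20 | × 0.82 | × 0.98 |

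Entries are median ratios of the HR after to before. This set-up yields about 43 events rather than 33, and the planned model is stratified, so the figures show scale only.

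**The case against.** The strongest reply is that the definition governs. SAP 2.5.1 and 2.5.3 censor only patients with no EFS event, and a patient in CRp or PR at the end of induction 2 has already met the definition. The sponsor's usage supports this: in Table 14-1 the footnote defines the event as no CR, and the only matching row is labelled *Treatment failure*, with components adding to the totals (125 + 98 + 21 = 244; 150 + 102 + 25 = 277). The label there covers the whole no-CR component. This stands, and it limits what may be inferred:

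- A reader might infer that the plan censors these patients. No section says so; it follows only from applying the table against the definition.
- A reader might infer that this trial's EFS departs from the A2301 EFS behind the prior. That holds only under the literal table. The estimate of 24 patients itself takes the Table 14-1 label as meaning no CR.
- A reader might place marrow-only persistent disease with CRp and PR. That rests on one 'and' in the resistant-disease wording; 7.2.1 elsewhere treats marrow blasts of 5% or more as residual leukemia. It is ambiguous.
- A reader might infer that miscoding under this SAP could overturn the success claim. SAP 2.5.2 notes that success was judged at the interim and/or primary analysis, not at the final one.

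Protocol 7.2.1 also provides for observation until count recovery with a repeat marrow when blasts are below 5%, so an early CRp need not be the final induction response.

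What the reply does not remove: even if treatment failure is shorthand for no CR, the shorthand conflicts with the definition in 7.2.1, and no rule explicitly dates a CRp or PR patient's event.

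**Conclusion.** The definition and its coding rule conflict, and the primary endpoint can be derived in more than one way. For CRp and PR this follows from the text alone; marrow-only disease is unclear. The documents do not show an intent to censor.

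The size is uncertain. The 2-7 patients rest on an assumed 10-30% share and on A2301 failure rates. If the affected patients are spread evenly, the HR changes by 1-2%, and equal shares of 10-50% cost about 1 to 5 points of success probability. Shifts of about 6-20% need one to three patients all in one arm.

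For the final analysis, the re-estimated HR and the Bayesian posterior of SAP 2.5.4 are exposed. For the success claim, the question is how the primary analysis coded these patients, since protocol Table 10-1 has the same row. The documents do not answer that. The point is worth correcting because it concerns the primary endpoint and the remedy is small.

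**What to change.** 1. In SAP Table 2-4, and in protocol Table 10-1, replace the row *Treatment failure* with: *No CR documented by end of induction 2 (CRp, PR, treatment failure, or induction stopped without CR): EFS event, date of randomization + 1*.
2. Use the same wording in SAP 2.5.1 in place of the treatment-failure sentence.
3. Point the response-criteria reference in SAP 2.5.1 to protocol 7.2.1 instead of SAP 2.7.1.
4. Tabulate the no-CR events by arm as CRp, PR, treatment failure or induction stopped without CR.
5. Confirm how the primary analysis coded these patients. If the final derivation differs, report the HR both ways and explain the difference.

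The cost is one table row, one sentence, one cross-reference and one small table. No new data are needed, because CRp and PR are already among the responses collected. Step 5 needs a check of the primary-analysis programs.
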